4.2 Exclusion criteria

ICH patients fulfilling **any** of the following criteria are **not** eligible for inclusion in this study:

1. Use of other investigational drugs within 5 half-lives of enrollment, or until the expected pharmacodynamic effect has returned to baseline (for biologics), whichever is longer.
2. History of hypersensitivity to any of the study drugs or to drugs of similar chemical classes (e.g., fingolimod).
3. Current use of concomitant medications with potent CYP2C9/3A4 inhibitory or induction potential.
4. *Intentionally blank – removed with protocol amendment #2.*
5. Infratentorial (midbrain, pons, medulla, or cerebellum) ICH.
6. Candidates for surgical hematoma evacuation or other urgent surgical intervention (i.e., surgical relief of increased intracranial pressure) on initial presentation. If during the treatment period surgical hematoma evacuation or surgical intervention to lower intracranial pressure becomes indicated, the investigational treatment should be stopped.
7. Patients with intraventricular hemorrhage (IVH) having a Graeb score (oGS) of >3 on initial presentation. Patients **must not** have blood in the 4th ventricle (0 points max), and may only have blood in the 3rd ventricle in the absence of ventricular expansion (≤ 1 point max). Trace or mild hemorrhage in either or both lateral ventricles (≤ 1 point each) is permitted. Patients with hydrocephalus determined radiographically on initial presentation are excluded regardless of oGS (see [Section 8.8](#)).
8. Secondary ICH due to:
 - aneurysm
 - brain tumor
 - arteriovenous malformation
 - thrombocytopenia, defined as platelet count of $<150,000/\mu\text{l}$
 - known history of coagulopathy
 - acute sepsis
 - traumatic brain injury (TBI)
 - disseminated intravascular coagulation (DIC)
9. Prior disability due to other disease compromising mRS evaluation, thereby interfering with the primary outcome, operationally defined as an estimated mRS score (by history) of ≥ 3 before ICH for patients ≤ 80 years of age. For ICH patients 81-85 years of age, estimated mRS by history prior to ICH **must** be ≤ 1 (no significant disability despite symptoms).

10. Preexisting unstable epilepsy.
11. Patients with active systemic bacterial, viral or fungal infections.
12. Concomitant drug-related exclusion criteria:
 - Intravenous immunoglobulin, immunosuppressive and/or chemotherapeutic medications.

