 - Moderate immunosuppressives (e.g. azathioprine, methotrexate) and/or fingolimod within 2 months prior to randomization.
 - Stronger immunosuppressives (e.g. cyclophosphamide, immunosuppressive mAb) within (minimally) 6 months prior to randomization, or longer with long-lasting immunosuppressive medications as determined by the investigator.
13. Cardiovascular exclusion criteria:
 - Cardiac conduction or rhythm disorders including sinus arrest or sino-atrial block, heart rate <50 bpm, sick-sinus syndrome, Mobitz Type II second degree AV block or higher grade AV block, or preexisting atrial fibrillation (either by history or observed at screening).
 - PR interval >220 msec. Long QT syndrome or QTcF prolongation >450 msec in males or >470 msec in females on screening electrocardiogram (ECG).
 - Patients receiving treatment with QT-prolonging drugs having a long half-life (e.g., amiodarone).
14. Any of the following abnormal laboratory values prior to randomization:
 - White blood cell (WBC) count < 2,000/ μ l (< 2.0×10^9 /L)
 - Lymphocyte count < 800/ μ l (< 0.8×10^9 /L)
15. Pregnant or nursing (lactating) women, where pregnancy is defined as the state of a female after conception and until the termination of gestation, confirmed by a positive hCG laboratory test.
16. Patients with any other medically unstable condition or serious laboratory abnormality as determined by the investigator.

The Investigator must ensure that all patients being considered for the study meet the inclusion criteria, above.

Patient selection is to be established by checking through all eligibility criteria at screening. A relevant record (e.g. checklist) of the eligibility criteria must be stored with the source documentation at the study site.

Deviation from any entry criterion excludes a patient from enrollment into the study.

5 Restrictions for Study Subjects

For the duration of the study, patients should be informed and reminded of the restrictions outlined in this section.

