5.2 Prohibited treatment

Use of medications displayed in [Table 5-1](#) are **NOT** allowed during treatment with BAF312 due to increased risk of immunosuppression, confounding of efficacy and/or potential interaction with study treatment (**NB**: CYP2C9 and CYP3A4 are the major metabolizing enzymes for BAF312).

Table 5-1 Prohibited Medications

Medication	Action to be taken
Immunosuppressive/chemotherapeutic medications or procedures, including cyclosporine, azathioprine, methotrexate, and immunomodulatory mABs	Stop taking. If not possible, consider discontinuation of study treatment
Medication that suppress AV conduction (e.g. carbamazepine, non-dihydropyridine calcium-channel blockers, or cardiac glycosides) with the exception of beta-blockers	Stop taking. If not possible, consider discontinuation of study treatment
Strong inhibitors of CYP2C9 or CYP3A4 (Table 21-1)	Stop taking. If not possible, consider discontinuation of study treatment Assess ECG and monitor lymphocyte counts
Potent inducers of CYP2C9 (Table 21-2)	Stop taking. If not possible, consider discontinuation of study treatment

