6.11 Concomitant treatment

Per U.S. and European stroke care guidelines, corticosteroids should not be used for treatment of ICH because they are ineffective and increase complications ([Hemphill et al 2015](#), [Steiner et al 2014](#)).

The Investigator must instruct the patient to notify the study site about any new medications he/she takes after the patient was enrolled into the study.

All prescription medications, over-the-counter drugs and significant non-drug therapies (including physical therapy and blood transfusions) administered or taken within the timeframe defined in the entry criteria prior to the start of the study and during the study, must be recorded on the Concomitant Medications/Significant Non-Drug Therapies CRF.

Medication entries should be specific to trade name, the single dose and unit, the frequency and route of administration, the start and discontinuation date and the reason for therapy.

Each concomitant drug must be individually assessed against all exclusion criteria/prohibited medication. If in doubt, the Investigator should contact Novartis before randomizing a patient or, if the patient is already enrolled, to determine if the patient should continue participation in the study.

7 Study completion and discontinuation

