7.2 Discontinuation of study treatment

Discontinuation of study treatment for a patient occurs when study treatment is stopped earlier than the protocol planned duration. Discontinuation of study treatment can be decided by either the patient or the Investigator.

Study treatment must be discontinued under the following circumstances or emergence of the following adverse events:

- Patient/guardian decision - patients may choose to discontinue study treatment for any reason at any time.
- The Investigator believes that continuation would negatively impact the safety of the patient or the risk/benefit ratio of trial participation.

- Severe hypersensitivity reaction occurs, including any of the following: anaphylaxis, fever, chills, urticaria, dyspnea, headache, myalgia, hypotension. Immediate interruption of the infusion to administer study treatment is required in such cases.
- Any protocol deviation that results in a significant risk to the patient's safety.
- Pregnancy (see [Section 8.6](#) (Safety) and [Section 9.6](#) (Pregnancy reporting))
- Use of prohibited treatment as per recommendations in [Table 5-1](#).
- If a liver or renal event occurs, follow guidelines outlined in [Appendix 1](#) and [Appendix 2](#) regarding discontinuation of study treatment.
- Any laboratory abnormalities that in the judgment of the Investigator, taking into consideration the patient's overall status, prevents the patient from continuing participation in the study.
- Expansion of initial ICH requiring surgical evacuation.
- Development of increased intracranial pressure requiring surgical intervention, including subsequent intraventricular expansion of the initial ICH leading to increased ventricular pressure requiring surgical management (e.g., EVD placement).
- Hemodynamically-significant bradycardia and/or 3rd degree AV block as described in [Section 6.6](#).

The appropriate personnel from the site and Novartis will assess whether investigational drug treatment should be discontinued for any patient whose treatment code has been broken inadvertently for any reason.

If discontinuation of study treatment occurs, the Investigator must determine the primary reason for the patient's premature discontinuation of study treatment and record this information on the CRF.

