Closed by local factor	✓	Non testable	NT

Verbal response

Criterion	Observed	Rating	Score
Correctly gives name, place and date	✓	Orientated	5
Not orientated but communication coherently	✓	Confused	4
Intelligible single words	✓	Words	3
Only moans / groans	✓	Sounds	2
No audible response, no interfering factor	✓	None	1
Factor interfering with communication	✓	Non testable	NT

Best motor response

Criterion	Observed	Rating	Score
Obeys 2-part request	✓	Obeys commands	6
Brings hand above clavicle to stimulus on head neck	✓	Localising	5
Bends arm at elbow rapidly but features not predominantly abnormal	✓	Normal flexion	4
Bends arm at elbow, features clearly predominantly abnormal	✓	Abnormal flexion	3
Extends arm at elbow	✓	Extension	2
No movement in arms / legs, no interfering factor	✓	None	1
Paralysed or other limiting factor	✓	Non testable	NT

Sites For Physical Stimulation

Features of Flexion Responses

Modified with permission from Van Der Naalt 2004
Ned Tijdschr Geneesk

For further information and video demonstration visit www.glasgowcomascale.org

Graphic design by Margaret Frey based on layout and illustrations from Medical Illustration 561 - 201002
© 2015 Graham Teasdale 2015

21 Appendix 7: List of prohibited medications

The aim of this document is to provide a specific list of drugs that should not be co-administered with BAF312 because of their CYP2C9/3A4 inhibitory or induction potential.

Due to the constant information arising on drugs, these lists are by no mean exhaustive and medical judgment should always prevail. These lists are adapted to the patient population and the exclusion criteria of the study CBAF312X2207 only.

Only potent CYP2C9 and CYP3A4 inhibitors may have a significant effect on BAF312 exposure and should not be co-administered with BAF312 (Table 21-1).

Potent CYP2C9 and/or CYP3A4 inducers (Table 21-2) should not be coadministered with BAF312 to avoid a potential decrease of efficacy of BAF312 in case of under-exposure due to CYP2C9/CYP3A4 induction (note that topical use is permitted).

Table 21-1 Typical inhibitors of CYP2C9 or CYP3A4

Antibiotics:	Antivirals:
Clarithromycin	Boceprevir
Sulfaphenazole	Telaprevir
Telithromycin	
Troleandomycin	
Protease Inhibitors:	Others:
Indinavir	Amiodarone
Lopinavir	Ataciguat
Nelfinavir	Azapropazone
Ritonavir	Benzbromarone
Saquinavir	Bucolome
Tipranavir	Cobicistat
Antifungals:	Conivaptan
Fluconazole	Elvitegravir
Itraconazole	Mibefradil
Ketoconazole	Nefazodone
Miconazole	Oxandrolone

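### No entry criterion bars a patient on a non-dihydropyridine calcium-channel blocker or cardiac glycoside that cannot be stopped, although Table 5-1 prohibits both during BAF312 treatment

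*Protocol*

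**What the plan says.** Protocol section 5.2 and Table 5-1 list four medication classes that are not allowed during treatment with BAF312. One is "Medication that suppress AV conduction (e.g. carbamazepine, non-dihydropyridine calcium-channel blockers, or cardiac glycosides) with the exception of beta-blockers". The action for that class is "Stop taking. If not possible, consider discontinuation of study treatment".

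The exclusion criteria in section 4.2 that concern these drugs are:

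- Criterion 3: "Current use of concomitant medications with potent CYP2C9/3A4 inhibitory or induction potential".
- Criterion 12: "Intravenous immunoglobulin, immunosuppressive and/or chemotherapeutic medications", with look-back periods for immunosuppressives.
- Criterion 13: cardiac conditions and ECG limits (heart rate below 50 bpm, PR above 220 msec, Mobitz II or higher block, atrial fibrillation, QTcF limits). It has one drug item, for QT-prolonging drugs with a long half-life, with amiodarone as the example.

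Two other sections bear on the point. Section 6.11 says "Each concomitant drug must be individually assessed against all exclusion criteria/prohibited medication", and asks the investigator to contact the sponsor before randomizing if in doubt. Section 7.2 lists, among the circumstances in which study treatment must be discontinued, "Use of prohibited treatment as per recommendations in" Table 5-1.

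**The concern.** A drug that is prohibited from the first dose would normally have a matching entry criterion, so that a patient who must stay on it is not randomized. For two of the drug groups named in the AV-conduction row there is none. A patient on one of them who cannot stop meets no listed exclusion, and the only instruction for that situation applies once study treatment is under way.

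The timing matters more for this class than for the others. Transient bradyarrhythmia and second-degree AV block are identified risks of starting BAF312 (section 1.3.1). Section 3.7 puts the heart-rate nadir about 3 to 4 hours after the first dose, and section 6.6 says these events typically occur within the first 48 hours. A decision to consider stopping BAF312, taken after dosing has begun, may fall within that window or after it. What is at stake is avoidable exposure of a few patients to two AV-slowing agents at once, and a protocol whose entry and on-treatment rules do not line up.

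**Working it through.** The plan states no figure on this point. The check is a comparison of texts, followed by an illustration of size.

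**1. Table 5-1 classes against the 16 exclusion criteria**

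| Table 5-1 class | Matching entry criterion |
|---|---|
| Immunosuppressive/chemotherapeutic | 12 |
| Strong CYP2C9 or CYP3A4 inhibitors | 3 |
| Potent CYP2C9 inducers | 3 |
| AV-conduction suppressants except beta-blockers | None for the class |

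**2. Drugs within the AV-conduction class**

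- Carbamazepine: listed in Table 21-2 as an inducer, so barred at entry by criterion 3.
- Amiodarone (not named in the row): named in criterion 13 and in Table 21-1, so barred at entry.
- Non-dihydropyridine calcium-channel blockers and cardiac glycosides: named in no criterion. Neither Appendix 7 list includes verapamil, diltiazem or digoxin. Appendix 7 does add that "these lists are by no mean exhaustive and medical judgment should always prevail", but its lists concern CYP effects, not AV conduction.

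**3. Does other text bar randomization when the drug cannot be stopped?**

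- Section 5.2 forbids use during treatment, but its instruction for a drug that cannot be stopped is to consider discontinuing study treatment. That presupposes a patient already on treatment and leaves continuation open.
- Section 6.11 requires an assessment and, in doubt, a call to the sponsor. It does not fix the outcome.
- Section 7.2 sits under a mandatory heading but refers back to Table 5-1, whose wording is optional.
- Criterion 16 covers unstable conditions and serious laboratory abnormalities, not co-medication.
- Section 4.2 states that deviation from any entry criterion excludes the patient. A prohibition placed only in section 5.2 does not carry that force.

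So detection is covered, while the bar on randomization is missing.

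**4. Size, on assumed inputs**

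The documents give neither the share of patients on such a drug (p) nor the share of users who cannot stop (f). Assume p = 0.01 to 0.06 and f = 0.10 to 0.50, and let q = p × f. The number of patients per arm is about 33 (section 4).

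| p | f | q | Expected, 33 × q | P(at least one) = 1 − (1 − q)^33 |
|---|---|---|---|---|
| 0.01 | 0.10 | 0.001 | 0.03 | 3% |
| 0.01 | 0.50 | 0.005 | 0.17 | 15% |
| 0.06 | 0.10 | 0.006 | 0.20 | 18% |
| 0.06 | 0.50 | 0.030 | 0.99 | 63% |

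These counts lean high, because the heart-rate, PR and atrial fibrillation limits in criterion 13 remove some users first. They count patients exposed, not patients harmed.

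**The case against.** The strongest reply is that the protocol already handles this. Section 5.2 does not allow these drugs during treatment, section 6.11 makes the site check every drug against the prohibited list, and section 7.2 opens with a mandatory rule. Read together, a site that randomizes a patient who must stay on a prohibited drug breaches section 5.2 at the first dose. On that view the remaining case is non-adherence rather than a gap in the design. Much of this stands, and it is why the point is minor. It does not close the gap: Table 5-1 itself provides for the drug that cannot be stopped and answers with an option, and no sentence tells the site not to randomize.

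A second reply is that the sponsor thought about AV-slowing drugs, since beta-blockers are expressly exempted, and chose ECG and condition limits that measure conduction with any drug on board. That is a fair reason to expect low risk. It does not explain why the remaining drugs are prohibited on treatment but not addressed at entry.

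Third, the absolute risk is low. Up-titration is said to avoid these effects completely (section 1.3.1) or almost completely (section 6.6). Monitoring runs from 1 hour before the first dose to at least 48 hours, with rules to stop, skip or discontinue. Section 6.6 reports that the FDA found this mitigation plan appropriate at pre-IND review. Section 3.3 notes that acute stroke patients are kept NPO until dysphagia is assessed, which will interrupt many oral drugs, though not intravenous ones. All of this stands.

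A reader might also infer that the whole AV-conduction class is open at entry, or that the five second-degree AV blocks in section 3.7 indicate the risk here. The documents support neither. Carbamazepine and amiodarone are barred, and those five cases arose in a study without dose titration.

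**Conclusion.** The point holds in a narrow form. A patient on a non-dihydropyridine calcium-channel blocker or cardiac glycoside that cannot be stopped meets no exclusion criterion, and the protocol's only specific instruction for that patient is optional and applies after treatment has begun. It is a minor safety and consistency point, worth a cheap correction.

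The size is not known. The figure of 0.03 to 1 patient in the BAF312 arm rests wholly on two assumed inputs and spans a 30-fold range, so it shows only that the number is small. The documents give no basis for sizing an added AV-conduction effect under titration.

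A reader might go further and infer a threat to the primary analysis, or that sites would enrol users of these drugs unchecked. Neither follows: nothing here touches the aPHE comparison, and section 6.11 requires the check.

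**What to change.** Add one item to exclusion criterion 13, and mirror it in the protocol summary and the eligibility checklist: *Current use of a drug that suppresses AV conduction (for example a non-dihydropyridine calcium-channel blocker or a cardiac glycoside; beta-blockers excepted) that cannot be stopped before the first infusion.*

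The cost is the added text and the loss of a small number of otherwise eligible patients, which the documents do not allow to be quantified. On the assumed inputs above it would be 65 × 0.001 = 0.07 to 65 × 0.03 = 1.95 of about 65 randomized.

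No extra ECG is proposed for patients who do stop such a drug. The ECG rows of Table 8-1 cannot be seen in the public text, and SAP section 8.2 already describes 12-lead ECGs at screening/baseline and on days 1 to 3, so a further pre-dose recording cannot be shown to be missing. The existing screening ECG limits and the cardiac monitoring that starts 1 hour before the first dose can be relied on.

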5.3 Dietary restrictions

- No grapefruit or grapefruit juice is to be consumed during the study until 7 days following the last dose (i.e., Day 21 after ICH).

5.4 Other restrictions

- No strenuous physical exercise (e.g. weight training, aerobics), not including formal rehabilitation therapy, until after Study Completion evaluation.

6 Treatment

6.1 Study treatment

Details on the requirements for storage and management of study treatment, and instructions to be followed for patient numbering, prescribing/dispensing and taking study treatment are outlined in the Site Operations Manual.

6.1.1 Investigational treatment and control drug(s)

Table 6-1 Overview of study medication

Study drug name	Formulation	Unit dose	Packaging	Provided by
BAF312/placebo	Film-coated Tablet	2 mg / 0 mg	Double blind kits	Novartis
BAF312/placebo	Concentrate for Solution for Infusion	4.5 mg /4.5 mL for BAF312; 0 mg/4.5mL for placebo	Double blind kits	Novartis

6.1.2 Additional study treatment

All patients will receive standard of treatment and care for patients with ICH according to the AHA/ASA ([Hemphill et al 2015](#)) and ESO Guidelines ([Steiner et al 2014](#)). No additional treatment beyond investigational treatment is required for this trial.

General Stroke Unit/Intensive Care Unit management throughout the study needs to be recorded on the Concomitant Medication eCRF. Post ICH rehabilitation, dates and therapy sessions should also be recorded on the same CRF.

6.2 Treatment arms

Patients will be assigned to one of the following 2 treatment arms in a ratio of 1:1.

Study treatments are defined as:

BAF312

Commercially Confidential Information

-OR-

Placebo

- Days 1 through 7: matching i.v. placebo
- Days 8 through 14; matching p.o. placebo QD

6.3 Treatment assignment and randomization

The randomization numbers will be generated using the following procedure to ensure that treatment assignment is unbiased and concealed from patients and investigator staff. A patient randomization list will be produced using a validated system that automates the random

assignment of patients to randomization numbers. These randomization numbers are linked to the different treatment arms, which in turn are linked to medication numbers. A separate medication list will be produced by or under the responsibility of Novartis Drug Supply Management using a validated system that automates the random assignment of medication numbers to packs containing the investigational drug(s).

The randomization scheme for patients will be reviewed and approved by a member of the sponsor Randomization Office.

Follow the details outlined in the Site Operations Manual regarding the process and timing of treatment assignment and randomization of patients.

6.4 Treatment blinding

This is a patient and investigator-blinded study. Patients and investigators will remain blinded to study treatment throughout the study, except where indicated below.

The identity of the treatments will be concealed by the use of study drugs that are all identical in packaging, labeling, schedule of administration, appearance, and odor.

Site staff

All site staff (including study investigators, coordinators, and nurses) will be blinded to study treatment throughout the study.

In this study, blinded, third-party Independent Raters will rate perihematoma edema (PHE) on CT images and mRS Scores from video-recorded interviews.

Unblinding a single patient at a site for safety reasons (i.e., necessary for patient management) will occur via an emergency system in place at the site (see [Section 6.7](#)).

Sponsor staff or delegate

The following unblinded sponsor roles are required for this study:

- Unblinded clinical staff managing drug re-supply to site.
- Unblinded PK sample analyst(s)

The independent statistician(s) and independent programmer(s) will be able to access the randomization list and treatment assignment information

Commercially Confidential Information

All unblinded personnel will otherwise keep randomization lists and data or information that could unblind other study team members confidential and secure except as described above.

Following final database lock all roles may be considered unblinded.

Table 6-2 Blinding levels

Role	Time or Event			
	Randomization list generated	Treatment allocation & dosing	Safety event (single subject unblinded)	Interim Analysis & dose escalation
Subjects/Patients	B	B	B	B
Site staff	B	B	B	B
Drug Supply and Randomization Office	UI	UI	UI	UI
Unblinded sponsor staff (see text for details)	B	UI	UI	UI
Independent statistician/statistical programmer/data analysts	B	UI	UI	UI
Independent DMC used for assessing interim safety results*	B	UI	UI	UI
All other sponsor staff not identified above	B	B	B	B

B - Remains blinded

UI - Allowed to be unblinded on individual patient level

* Semi-blinded by treatment group (Group A, Group B, etc.) unless and until a between-group safety imbalance is seen by DMC (see [Section 11.9](#) Interim analyses).

